5.5. Immunogenicity Analysis Set

The immunogenicity analysis set is defined as all enrolled subjects who receive at least 1 dose of investigational product and have at least 1 post-treatment measurement of immunogenicity parameters of interest (ie, ADA [anti-PF-06817024 antibody] or NAb [Neutralizing anti-PF-06817024 antibody]).

CCI

5.7. Treatment Misallocations

All analyses will be performed on an "as-treated" basis and will not include data from subjects who are randomized but not treated.

If a subject takes a treatment that is not consistent with the treatment they are randomized to, for example takes a treatment out of sequence or takes the same treatment twice, then they will be reported under the treatment that they actually receive for all safety, PK and analyses, where applicable.

5.8. Protocol Deviations

Subjects who experience events that may affect their PK profile (eg, vomiting) may be excluded from the PK analysis. At the discretion of the pharmacokineticist, a concentration value may also be excluded if the deviation in sampling time is of sufficient concern or if the concentration is anomalous for any other reason.

At the discretion of the clinical team, a value may also be excluded if the deviation collection / procedure time is of sufficient concern or if the concentration is anomalous for any other reason.

A full list of protocol deviations will be compiled and reviewed to identify major and minor deviations prior to database closure.

5.8.1. Deviations Assessed Prior to Randomization

At screening, the investigator will assess subjects against the inclusion and exclusion criteria as set out in Sections 4.1 and 4.2 of the protocol.

5.8.2. Deviations Assessed Post-Randomization

Any significant deviation from the protocol will be reviewed prior to database closure and a decision taken regarding evaluation for each analysis population.

CCI		
CCI		
CCI		

6.2. Safety Endpoints

In this section, the safety endpoints that will be measured during the study are detailed. Where applicable, details of the endpoints to be derived and definition of baseline are also provided.

The following data are considered in standard safety summaries (see protocol for collection days and list of parameters):

• Adverse events;

- Laboratory data;
- Vital signs data;
- ECG results.

6.2.1. Adverse Events

Any events occurring following start of treatment or increasing in severity after randomization will be counted as treatment emergent.

Events that occur in a non-treatment period (for example, washout or follow-up) will be counted as treatment emergent and attributed to the previous treatment taken.

6.2.2. Laboratory Safety Tests

Safety laboratory tests will be performed as described in the protocol.

To determine if there are any clinically significant laboratory abnormalities, the hematological, clinical chemistry (serum) and urinalysis safety tests will be assessed against the criteria specified in the sponsor reporting standards. The assessment will take into account whether each subject's baseline test result is within or outside the laboratory reference range for the particular laboratory parameter.

Baseline will be the last pre-dose measurement of Day 1.

6.2.3. Vital Signs

Single supine blood pressure, pulse measurements and temperature will be taken at times detailed in the Schedule of Activities given in the protocol.

The last pre-dose measurement at Day 1 will be used as the baseline, subjects with a second dose will not be re-baselined. The maximum increase from baseline will be calculated by first subtracting the baseline value from each post-dose measurement to give the change from baseline. The maximum of these values over the respective period will then be selected, except in the case where a subject does not show an increase. In such an instance, the minimum decrease should be taken.

Similarly, the maximum decrease from baseline will be determined by selecting the minimum value of the changes from baseline. In cases where a subject does not show a decrease, the minimum increase should be taken.

6.2.4. ECG

A single or triple 12-lead ECG will be obtained on all subjects at times detailed in the Schedule of Activities given in the protocol. The average of the triplicate readings collected in Part 1 at each assessment time will be calculated for each ECG parameter. Baseline will be defined as the average of the triplicate pre-dose recordings at Day 1, for Parts 2 and 3, the last measurement prior to first dose will be used as the baseline.

The QT, QTc, PR, RR, QRS and heart rate will be recorded at each assessment time.

If not supplied, QTcF will be derived using Fridericia's heart rate correction formula:

$$QTcF = QT / (RR)^{1/3}$$
 where $RR = 60/HR$ (if not provided)

If not supplied, QTcB will be derived using Bazett's heart rate correction formula:

$$QTcB = QT / (RR)^{1/2}$$
 where $RR = 60/HR$ (if not provided)

The maximum increase from baseline will be calculated by first subtracting the baseline value from each postdose measurement to give the change from baseline. The maximum of these values over the respective period will then be selected, except in the case where a subject does not show an increase. In such an instance, the minimum decrease should be taken.

6.2.5. Other Safety Data

Additional safety data will be collected as described in the protocol and will be listed if collected in the sponsor's database.

6.3. Pharmacokinetic Endpoints

Blood samples for PK analysis of PF-06817924 will be taken according to the Schedule of Activities given in the protocol.

The following PK parameters will be calculated for PF-06817024 (if possible) from the concentration-time values using standard non-compartmental methods for Parts 1, 2 and 3.

[figure not shown]
Parameter	Analysis Scale	PF-06817024
Single Dose †	•	
AUC _{last}	ln	D
AUC _{inf} *	ln	D
$AUC_{inf}(dn) *$	ln	D
C _{max}	ln	D
$C_{max}(dn)$	ln	D
T _{max}	R	D
t _{1/2} *	R	D
CL (IV only) *	ln	D
V _{ss} (IV only) *	ln	D
CL/F (SC only) *	ln	D
Vz/F (SC only) *	ln	D
Multiple Dose ‡		
AUC _{tau}	ln	D
AUC_{tau} (dn)	ln	D
C _{av}	ln	D
C _{max}	ln	D
$C_{max}(dn)$	ln	D
T _{max}	R	D
t _{1/2} *	R	D
C _{min}	ln	D
R _{ac} AUC _{tau}	ln	D
R _{ac} C _{max}	ln	D

Table 1Non-compartmental PK Parameters

D = displayed with descriptive statistics, ln = natural-log transformed, R = raw (untransformed), * = if data permit, $\dagger =$ single dose subjects in Part 1 and all subjects in Part 2, $\ddagger =$ multiple dose subjects in Part 1 and all subjects in Part 3, tau = dosing interval for multiple dosing.

CCI		F
CCI		
1		
CCI		
CCI		
CCI		

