1.2.5.2. PK Data

Based on a preliminary, draft dataset obtained in January 2018 and including interim data from subjects in the first two parts of the study, a non-compartmental PK analysis was performed and the derived PF-06817024 PK parameters are summarized descriptively in Table 1.

Following single IV doses in healthy subjects, the median time for occurrence of maximal concentration (T_{max}) ranged between 1.76 and 3 hours, while the median T_{max} after SC administration (30 mg) was 338 hours (\approx 14 days). PF-06817024 had a prolonged half-life ($t_{1/2}$) with mean values ranging from 79 to 94 days across all single dose healthy volunteer cohorts. Both maximal plasma concentration (C_{max}) and area under the concentration-time curve from time 0 to infinity (AUC $_{inf}$) appeared to be approximately dose proportional in healthy subjects across the 10-1000 mg IV range (see Table 1), indicating that PF-06817024 exhibits linear kinetics in humans within this dose range. Clearance (CL) values (geometric mean) ranged from 0.00206 L/h to 0.00259 L/h across all single IV dose healthy volunteer cohorts. Using the calculated geometric means of AUC $_{inf}$ after single IV infusion and SC administration of the same dose (30 mg) in healthy subjects (8579/14590, see Table 1), the bioavailability (F) after SC administration is approximately 59% relative to IV infusion.

Multiple dose PK data were available only for 4 healthy subjects from the 100 mg IV cohort who received an additional 100 mg IV dose. The (geometric) mean C_{max} after the second dose was 42.47 µg/mL (geometric CV of 11%) across these 4 subjects and the associated median T_{max} was 1.54 hours. The (geometric) mean area under the concentration-time curve from the time of the second dose until 720 hours post-dose (AUC_{τ}) and until infinity (AUC_{inf}) was 16540 (geometric CV of 13%) and 73400 µg•hr/mL (geometric CV of 23%) respectively. Finally, the mean calculated $t_{1/2}$ after the second dose was 108 days (standard deviation (SD) of 10).

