Part 3 is a placebo-controlled, double blind, pharmacist and sponsor open, cohort to evaluate safety, tolerability, PK, immunogenicity, of repeat doses of PF-06817024 administered to subjects with moderate to severe AD. Approximately 20 subjects are planned to be enrolled in this cohort. Subjects will be randomized to receive PF-06817024 or placebo in a 3: 1 ratio (PF-06817024: placebo). Additional subjects up to a total of approximately 32 may be enrolled in a 3: 1 ratio (PF-06817024: placebo).

Subjects randomized to PF-06817024 will receive a loading dose of 600 mg IV on Day 1, followed by 3 doses of 300 mg IV every 4 weeks (last dose being on Week 12). Placebo subjects will receive 4 IV doses of matching placebo every 4 weeks. This dosing regimen is expected to decrease the time to steady state

exposure and provide nearly complete target coverage based on currently available in vitro and clinical data.

1.3.1.3. Parts 1, 2, and 3

The duration of the follow-up is selected to be at least 1 year after the last dose of study drug (at Week 12 for Part 3), which is ≥ 3 times the preliminary estimated half-life of approximately 90 days and > 80% exposure (AUC) based on emerging data for the earlier cohorts of healthy subjects, which is adequate to estimate the elimination half-life. If the emerging data project that pharmacologically relevant exposure will extend significantly longer than 1 year, the subjects will be asked to return for extended follow-up visit(s) at up to 3 month intervals beyond the last planned regular visit until one of the following criteria has been met:

• The follow up period from the last dose of study drug is approximately ≥5 times the observed half-life; OR

• The period since the last dose of study drug is of sufficient duration to have projected exposures decrease below ADA drug tolerance levels; OR

The Sponsor will inform the sites when subjects may be discharged from the study based on review of emerging data indicating that one or more of the above criteria are met. Current guidance is that subjects will be in the study for 5 half-lives ie, about 450 days from the last dose.

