As discussed in Section 1.2.5.2 and presented in Table 1, the emerging clinical data from cohorts in Part 1 show that the half-life of PF-06817024 is approximately 79-94 days. Preliminary modeling using interim PK data available at the time of Protocol Amendment 4 from the healthy subject cohorts suggested that monthly dosing of PF-06817024 may be required for continuous, high level, suppression of IL-33 levels, despite the long half-life of PF-06817024. In order to shorten the onset of suppression of IL-33 levels a 600 mg loading dose of PF-06817024 is proposed in this study. The proposed dose of PF-06817024, the number doses, and/or the dosing interval may be modified in light of emerging safety, tolerability, PK,

Assuming that PF-06817024 PK is similar between healthy subjects and AD patients, the average concentration (C_{av}) during the first and the last dosing interval of the proposed dosing regimen was predicted to be 84.1 µg/mL and 132.5 µg/mL respectively. Thus, the proposed dosing paradigm will provide safety margins of approximately 5.3-fold and 3.3-fold relative to the 600 mg loading dose and the third dose of 300 mg (due to accumulation the margin for 300 mg is less than the 600 mg), respectively, with respect to the toxicokinetic stopping limit of C_{av} =442.5 µg/mL.

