9. DATA ANALYSIS/STATISTICAL METHODS

Detailed methodology for summary and statistical analyses of the data collected in this study are outlined here and further detailed in a Statistical Analysis Plan (SAP), which will be maintained by the sponsor. The Statistical Analysis Plan may modify what is outlined in the protocol where appropriate; however, any major modifications of the primary endpoint definitions or their analyses will also be reflected in a protocol amendment.

The study will be divided into two parts. Part 1 is the healthy subject section while Part 2 will include the patient cohorts. Results of Parts 1 and 2 will be summarized and displayed in separate tables when appropriate. Results from the SAD and multiple dose portions of Part 1 may also be displayed in separate tables as appropriate.

An additional Part 3 with AD subjects is included as part of Protocol Amendment #4. Results will be summarized and displayed in separate tables when appropriate.

In addition, summarizations of unblinded preliminary safety, PK, CCI may be performed for each part after Week 12 safety, PK, and have been obtained from a majority of subjects in that Part, as applicable, but prior to the end of the study and full safety follow-up. Further details will be defined in the SAP.

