9.3. Pharmacokinetic Analysis

The PK concentration population will be defined as all randomized subjects who received at least 1 dose of PF-06817024 and in whom at least 1 concentration value is reported. The PK parameter analysis population is defined as all enrolled subjects who received at least 1 dose of PF-06817024 and in whom at least one of the PK parameters of interest is calculated.

PK parameters for PF-06817024 following single and multiple dose administration will be derived from the concentration-time profiles by non-compartmental analysis. The PK parameters are defined in Table 9.

Table 9. Definition of PK Parameters in Study C03	641001
---	--------

Parameter	Definition	Period†	Method of Determination
C _{max}	Maximum serum concentration	SD/MD	Observed directly from data
$C_{max}(dn)$	Dose normalized C _{max}	SD/MD	C _{max} /Dose
C_{\min}	Trough serum concentration	MD	Observed directly from data
T_{max}	Time for C _{max}	SD/MD	Observed directly from data as time of first occurrence
AUC _{last}	Area under the plasma concentration-time profile over the dosing interval τ	SD	Linear/Log trapezoidal method
AUC _{inf} *	Area under the plasma concentration-time profile from zero to infinity	SD	Linear/Log trapezoidal method
AUC _{tau}	Area under curve within dosing interval, $\tau = 720$ hr for single dose cohort	MD	Linear/Log Trapezoidal method

Table 9. Definition of PK Parameters in Study C0341001

Parameter	Definition	Period†	Method of Determination
AUC _{tau} (dn)	Dose normalized AUC _{tau}	MD	AUC _{tau} /Dose
C _{av}	Average concentration over dosing interval	MD	AUC _{tau} /tau
CL* (IV only)	Clearance	SD	Dose / AUC _{inf}
Vss* (IV only)	Volume of distribution at steady state	SD	AUMC _{inf} /AUC _{inf} *CL
CL/F* (SC only)	Apparent clearance	SD	Dose/AUC _{inf}
Vz/F* (SC only)	Apparent volume of distribution	SD	Dose/(AUC _{inf} k _{el})
t _{1/2} *	Terminal elimination half-life	SD/MD	$Log_e(2)/k_{el}$, where k_{el} is the terminal phase rate constant calculated by a linear regression of the log-linear concentration-time curve. Only those data points judged to describe the terminal log-linear decline will be used in the regression.
R _{ac,} AUCtau	Accumulation ratio for AUC _{tau}	MD	AUC _{tau} last dose/AUC _{tau} first dose
$R_{ac,}C_{max}$	Accumulation ratio for C_{max}	MD	C _{max} last dose/C _{max} first dose

[figure not shown]

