8. STATISTICAL METHODOLOGY AND STATISTICAL ANALYSES

8.1. Statistical Methods

As this is an exploratory study, no formal hypothesis testing will be performed. CCI

Statistical Analyses

All efficacy data from parts 1, 2 and 3will be listed and summarized separately. Safety data will also be summarized combining all three parts as well as separately. Percentages will be presented to one decimal place in all summaries. Minimum and maximum values will be presented to the same number of decimal places as collected on the CRF or with the laboratory screening panel; mean and median will be presented to one further decimal place; standard deviations will be presented to two further places.

In data presentations, results will be sorted by increasing dose level and by study part (SAD/MAD, Nasal Polyps, or Atopic Dermatitis) as appropriate.

Binary variables will be summarized by the number of responders and the number of subjects with data. Percentages will be presented for both observed cases (number of subjects with data at the time point for the denominator) and by non-response imputation (NRI) (number of subjects with data at baseline in the denominator).

Pharmacokinetic Analysis

To assess the pharmacokinetics of PF-06817024, the PK parameters detailed in Section 6.3 will be listed and summarized for subjects in the PK analysis set (as defined in Section 5.2.2). Missing values will be handled as detailed in Section 7. Each PK parameter will be summarized by cohort and will include the set of summary statistics as specified in the table below:

Type of Dosing	Parameter	Summary Statistics
Single Dose [†]	AUC _{last} , AUCinf, AUCinf (dn), C _{max} ,	N, arithmetic mean, median, cv%,
	Cmax(dn), CL, Vss, CL/F, Vz/F	standard deviation, minimum,
		maximum, geometric mean and
		geometric cv%.
	T _{max}	N, median, minimum, maximum.
	t _{1/2}	N, arithmetic mean, median, cv%,
		standard deviation, minimum,
		maximum.
Multiple Dose‡	AUC _{tau} , AUCtau (dn), C _{av} , C _{max} ,	N, arithmetic mean, median, cv%,
	C _{max} (dn), Cmin, Rac AUCtau, Rac	standard deviation, minimum,
	C _{max}	maximum, geometric mean and
		geometric cv%.
	T _{max}	N, median, minimum, maximum.
	t _{1/2}	N, arithmetic mean, median, cv%,
		standard deviation, minimum,
		maximum.

Table 2. PK Parameters to be Summarized Des	scriptively
---	-------------

 \dagger = single dose subjects in Part 1 and all subjects in Part 2, \ddagger = multiple dose subjects in Part 1 and all subjects in Part 3.

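### Part 3 accumulation ratios: the only visible Rac formula has no dose term, yet Part 3 goes from a 600 mg first dose to a 300 mg last dose

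*SAP*

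**What the plan says.** - **SAP 6.3, Table 1.** The Multiple Dose block lists Rac AUCtau and Rac Cmax beside AUCtau, AUCtau(dn), Cav, Cmax, Cmax(dn), Tmax, t1/2 and Cmin. Its double-dagger footnote applies the whole block to "multiple dose subjects in Part 1 and all subjects in Part 3, tau = dosing interval for multiple dosing".
- **SAP 8.1, Table 2.** The multiple-dose row again contains the ratios ("Cmin, Rac AUCtau, Rac" and so on), with the same scope. No formula for Rac is visible in the SAP.
- **Protocol 9.3, Table 9.** This table defines the study's PK parameters. Rac for AUCtau is "AUC _{tau} last dose/AUC _{tau} first dose", and Rac for Cmax has the same form. Neither contains the dose.
- **Protocol 1.3.1.2.** Part 3 active subjects receive "a loading dose of 600 mg IV on Day 1, followed by 3 doses of 300 mg IV every 4 weeks". SAP 2.3 gives the same regimen.
- **Protocol 2.2.2.** Rac appears only under the Part 1 multiple-dose cohorts, where the last dose is the second. The Part 3 PK endpoint is concentrations.
- **Protocol 1.3.2.3.** For Part 3, average concentration "during the first and the last dosing interval of the proposed dosing regimen was predicted to be 84.1" µg/mL and 132.5 µg/mL respectively. The text attributes the smaller margin at the later 300 mg dose to accumulation.

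**The concern.** An accumulation ratio of last over first exposure can be read as accumulation only if the two doses are equal or the values are divided by dose. Cohort 3 in Part 1 meets the first condition (100 mg twice). Part 3 does not: the numerator follows 300 mg and the denominator follows 600 mg. The SAP extended Rac to Part 3 without adapting the definition, and nothing visible says that Rac is to be built from AUCtau(dn) and Cmax(dn).

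A programmer following the only written formula would report a Part 3 ratio that mixes accumulation with the halving of the dose. For Cmax the two effects roughly cancel, so the table could show little or no accumulation for a drug with a half-life of about three months given every four weeks.

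**Working it through.** **1. Reproduce the protocol's own figures.** Against the Cav limit of 442.5 µg/mL, 442.5/84.1 = 5.26 and 442.5/132.5 = 3.34. These match the stated margins of 5.3 and 3.3, so the two Cav values are read correctly.

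**2. Effect of omitting the dose.** The dose-normalised ratio is (last/300)/(first/600) = 2 × (last/first). The factor of 2 is exact, for AUCtau and Cmax alike, whatever the PK model.

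**3. Rac AUCtau.** Cav = AUCtau/tau and each interval is four weeks, so the ratio of Cav values equals the ratio of AUCtau values.
- As written: 132.5/84.1 = 1.58.
- Dose-normalised: 2 × 1.5755 = 3.15.

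**4. Rac Cmax, by superposition.** This assumes linear PK (Protocol 1.2.5.2, 10-1000 mg IV) and similar PK in AD and healthy subjects (Protocol 1.3.2.3). The half-life is taken from Protocol 1.2.5.2: "with mean values ranging from 79 to 94 days across all single dose healthy volunteer cohorts".
- Cav in the first interval after 300 mg alone: 84.1/2 = 42.05 µg/mL.
- Carry-over Cav in the last interval: 132.5 − 42.05 = 90.45 µg/mL.
- Concentration just before the last dose: 90.45 / [(1 − e^(−28k))/(28k)], with k = ln 2/t1/2. The bracket is 0.887 at 79 days and 0.904 at 94 days, which gives 102.0 and 100.1 µg/mL.
- Ratio as written: (300 × Cmax(dn) + trough)/(600 × Cmax(dn)) = 0.5 + trough/(600 × Cmax(dn)).

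With Cmax(dn) from Protocol Table 1 (µg/mL/mg):

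| IV cohort | Cmax(dn) | As written | Dose-normalised |
|---|---|---|---|
| 100 mg, healthy | 0.3544 | 0.97-0.98 | 1.94-1.96 |
| 300 mg, healthy | 0.3249 | 1.01-1.02 | 2.03-2.05 |
| 1000 mg, healthy | 0.3132 | 1.03-1.04 | 2.07-2.09 |
| 300 mg, CRSwNP | 0.2994 | 1.06-1.07 | 2.11-2.14 |
| 30 mg, healthy | 0.4091 | 0.91-0.92 | 1.82-1.83 |
| 10 mg, healthy (CV 51%) | 0.2395 | 1.20-1.21 | 2.39-2.42 |

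The 100-1000 mg cohorts, including CRSwNP, give 0.97-1.07 as written against 1.94-2.14. All IV cohorts give 0.91-1.21 against 1.8-2.4.

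**5. Does dose normalisation recover equal-dose accumulation?** Not fully, because the 600 mg dose leaves more residual drug than a 300 mg dose would. In a one-compartment check at 79-94 days, the dose-normalised AUCtau ratio is 3.35-3.55, against 2.87-3.01 for four equal doses. The excess is 16.7-17.9%. Scaling the carry-over to the protocol's Cav values gives an equal-dose ratio of 2.71-2.70, so 3.15 exceeds it by 16.1-16.8%.

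**The case against.** **The SAP never says that Table 9 governs Part 3.** It refers only to standard non-compartmental methods, and Protocol 2.2.2 confines Rac to Part 1. On this view the gap is an unstated definition, not a wrong one. This does not remove the point: Table 9 is presented as the study's definition of PK parameters and is the only visible Rac formula. Some SAP text is redacted, so only visible is as far as the claim goes.

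**The reader is partly protected.** SAP 8.1 plans one PK summary table per Part, with dose information in the treatment subheading, and Cmax(dn) and AUCtau(dn) are in the same block. This stands and limits the harm. It does not correct a ratio labelled accumulation that spans two dose levels.

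**The undivided ratio has a meaning.** It shows how maintenance exposure compares with loading exposure. That is true, but it would need a different label.

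**The sizes are predictions.** The AUCtau figures come from modelled Cav. The planned analysis would have a Day 8 sample in the first interval but no visit between Day 85 and Day 113 in the last. This also stands.

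A reader might infer more than the documents support:
- *That the SAP had no right to add Rac to Part 3.* Protocol 9 allows it ("The Statistical Analysis Plan may modify what is outlined in the protocol where appropriate"), and Part 3 has a repeat-dose PK objective.
- *That Part 1 and Part 3 would visibly conflict, about 1.2 against 1.0.* The 1.2 divides a mean Cmax that "after the second dose was 42.47" µg/mL in four subjects by 35.44 µg/mL in a different set of seven. The second dose could follow at 4 to 12 weeks, and the Parts are tabulated separately. This is not evidence of harm.
- *That accumulation would be hidden altogether.* Rac AUCtau as written would still exceed 1.

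**Conclusion.** The point holds and is minor. Taken with the only visible definition, Part 3 Rac equals exactly half the dose-normalised ratio: 1.58 against 3.15 for AUCtau, and near 1 against about 2 for Cmax. The factor of 2 depends only on the 600 mg and 300 mg doses. The levels rest on the protocol's predicted Cav, linear PK, AD subjects resembling healthy ones, and preliminary half-life and Cmax(dn) values. The Cmax level also depends on which cohorts are used, so it is a rough centre and not a precise estimate.

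No conclusion of the study turns on it. The SAP tests no hypotheses and has no statistical decision rules (SAP 4.1, 4.2), and the PK stopping limit is set on Cav (Protocol 3.2). What is at stake is a descriptive Part 3 entry that could suggest little or no accumulation where the protocol expects it.

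**What to change.** Leave the double-dagger footnote as it is, so that Part 3 keeps all the other multiple-dose parameters. Give the two Rac entries their own marker in SAP Table 1 and their own row in SAP Table 2. Under that marker:

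- **Preferred:** limit Rac to Part 1 multiple-dose subjects, consistent with Protocol 2.2.2.
- **Alternative:** define Part 3 Rac as AUCtau(dn) last / AUCtau(dn) first and Cmax(dn) last / Cmax(dn) first, each normalised to the dose given at that visit. Fix last as the fourth dose (Day 85) and include only subjects who received all four doses, so that early stoppers are not pooled in. Add a footnote that loading-dose carry-over makes the AUCtau ratio about 16-18% higher than equal-dose accumulation, and that it is not comparable with the two-dose Part 1 ratio.

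The cost is one marker with its footnote and one table row. No new data or parameters are needed, because the dose-normalised values are already listed. The change concerns the analysis definition only.
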